8.2 Study product formulation

DNA-HIV-PT123 (labeled as DNA-HIV-PT123 [4 mg/mL]) is supplied as a 4 mg/mL DNA solution in a 2 mL sterile glass vial containing a volume to deliver 1 mL of a clear, colorless solution. The product must be stored at -20° C +/- 5° C.

The study product is described in further detail in the Investigator's Brochure (IB).

Placebo for DNA-HIV-PT123 (Sodium Chloride for Injection, 0.9%)

Sodium Chloride for Injection, 0.9%, will be used as the placebo for DNA-HIV-PT123. Product must be stored as directed by the manufacturer.

Bivalent Subtype C gp120 composed of two different proteins:

TV1.C gp120 protein [labeled as TV1.C gp120]: The TV1.C gp120 protein will be provided in a glass vial containing approximately 0.58 mL (800 mcg/mL) of protein in buffer. The protein is a clear colorless to slightly yellow liquid when thawed. The product must be stored frozen at -61°C or colder. Once thawed, the study product should be used immediately or stored in refrigerator at 2 to 8°C, for no longer than 24 hours. Unused vials should be quarantined after this time.

1086.C gp120 protein [labeled as 1086.C gp120]: The 1086.C gp120 protein will be provided in a glass vial containing approximately 0.58 mL (800 mcg/mL) of protein in buffer. The protein is a clear colorless to slightly yellow liquid when thawed. The product must be stored frozen at -61°C or colder. Once thawed, the study product should be used immediately or stored in refrigerator at 2 to 8°C, for no longer than 24 hours. Unused vials should be quarantined after this time.

The study product is described in further detail in the IB.

MF59 [labeled as MF59C.1] is supplied as an oil-in-water emulsion. The MF59 adjuvant has a milky white opaque appearance and is provided in a glass vial containing a total volume of 0.7 mL. The product must be stored refrigerated at 2 - 8° C. Do not freeze.

The study product is described in further detail in the Investigator's Brochure (IB).

 $AS01_B$ is produced as a liposomal formulation containing MPL and QS-21. It is provided as an opalescent colorless to yellowish liquid in pre-filled vials. Each vial contains a volume to deliver 0.5 mL. The product must be stored refrigerated at 2 to 8° C.

The study product is described in further detail in the IB.

Placebo for Bivalent Subtype C gp120 / MF59 (Sodium Chloride for Injection, 0.9%)

Sodium Chloride for Injection, 0.9%, will be used as the placebo for Bivalent Subtype C gp120 / MF59. Product must be stored as directed by the manufacturer.

Placebo for Bivalent Subtype C gp120 / AS01_B (Sodium Chloride for Injection, 0.9%)

Sodium Chloride for Injection, 0.9%, will be used as the placebo for Bivalent Subtype C gp120 / $AS01_B$. Product must be stored as directed by the manufacturer.

8.3 Preparation of study products

Pharmacists should refer to USP 38 General Chapter Physical Tests / <797> Pharmaceutical Compounding - Sterile, and should follow the requirements of their country, their institution, and their pharmacy regulatory authority regarding these procedures. At a minimum, study products must be prepared in a biological safety cabinet/isolator by appropriately trained/qualified pharmacy personnel using aseptic technique.

8.3.1 DNA-HIV-PT123

One vial of DNA-HIV-PT123 (labeled as DNA-HIV-PT123 [4 mg/mL]) will be needed to prepare the dose. Prior to dispensing, the pharmacist will remove the study product from the freezer and allow it to thaw at room temperature.

Once thawed, the pharmacist, using aseptic technique, will gently swirl the vial and then withdraw 1 mL into a syringe. The syringe should be no smaller than 1.5 mL syringe and no larger than a 5 mL syringe.

The syringe should be labeled as "DNA 4 mg or Placebo 1 mL" and have an overlay to maintain blinding. The syringe must also be labeled for administration in the LEFT deltoid. The study product should be administered as soon as possible after preparation.

Any partial vials or expired filled syringes should be autoclaved immediately prior to disposal and disposed of in accordance with institutional or pharmacy policy.

8.3.2 Placebo for DNA

Using aseptic technique, the pharmacist will withdraw 1 mL of Sodium Chloride for Injection, 0.9% into a syringe. The syringe should be no smaller than 1.5 mL syringe and no larger than a 5 mL syringe.

The syringe should be labeled as "DNA 4 mg or Placebo 1 mL" and have an overlay to maintain blinding. The syringe must also be labeled for administration in LEFT deltoid. The study product should be administered as soon as possible after preparation.

Any unused portion of entered vials or expired prefilled syringes should be disposed of in accordance with institutional or pharmacy policy.

8.3.3 Bivalent Subtype C gp120 / MF59 (an admixture of 100 mcg of TV1.C gp120, 100 mcg of 1086.C gp120, and MF59C.1)

One vial of TV1.C gp120 protein, 1 vial of 1086.C gp120 protein, and 1 vial of MF59C.1 will be needed to prepare the dose. Prior to dispensing, the pharmacist will remove the TV1.C gp120 and 1086.C gp120 from the freezer and allowed to thaw at room

temperature. The pharmacist will also remove the MF59C.1 vial from the refrigerator and mix by repeated gentle swirling and inversion (do not shake vigorously).

Using aseptic technique, the pharmacist will gently swirl the contents of the vial containing TV1.C gp120 and then withdraw 0.35 mL of TV1.C gp120 from the correct vial and inject it into the vial containing MF59C.1. The pharmacist will then gently swirl the vial containing 1086.C gp120 after which, using aseptic technique, the pharmacist will withdraw 0.35 mL of 1086.C gp120 from the correct vial and inject it into the MF59C.1 vial (which contains TV1.C gp120 and MF59C.1). After gentle swirling and inversion (do not shake vigorously) the pharmacist, using aseptic technique, will withdraw 0.5 mL of the mixed preparation for dosing into a 3 mL syringe or smaller. The needle should be removed and the syringe capped.

The syringe should be labeled as "Bivalent Subtype C gp120 / MF59 or Placebo 0.5 mL" and have an overlay to maintain blinding. The syringe must also be labeled for administration in RIGHT deltoid. The syringe containing study product should be bagged for transport to the clinic where it will be administered. This study product should be administered immediately, defined as within 30 minutes as per IAC recommendations. If this is not possible, the site pharmacist may be permitted to label the syringe with a DO NOT USE AFTER 2 hour date and time from preparation. In this case, the vaccine should be stored at 2°C - 8°C until administration and if not used within 2 hours, it should be discarded.

Any unused portion of reconstituted vials or expired prefilled syringes is disposed of in accordance with institutional or pharmacy policy for a biological safety level S1 product.

8.3.4 Placebo for Bivalent Subtype C gp120 / MF59

Using aseptic technique, the pharmacist will withdraw 0.5 mL of Sodium Chloride for Injection, 0.9% into a 3 mL or smaller syringe. The needle should be removed and the syringe capped.

The syringe should be labeled as "Bivalent Subtype C gp120 / MF59 or Placebo 0.5 mL" and have an overlay to maintain blinding. The syringe must also be labeled for administration in RIGHT deltoid. The syringe containing study product should be bagged for transport to the clinic where it will be administered. This study product should be administered immediately, defined as within 30 minutes as per IAC recommendations. If this is not possible, the site pharmacist may be permitted to label the syringe with a DO NOT USE AFTER 2 hour date and time from preparation. In this case, the vaccine should be stored at 2°C - 8°C until administration and if not used within 2 hours, it should be discarded.

Any unused portion of entered vials or expired prefilled syringes should be disposed of in accordance with institutional or pharmacy policy.

8.3.5 Bivalent Subtype C gp120 / $AS01_B$ (an admixture of 100 mcg of TV1.C gp120, 100 mcg of 1086.C gp120, and $AS01_B$)

One vial of TV1.C gp120 protein, one vial of 1086.C gp120 protein, two vials of $AS01_B$, and one empty sterilized vial (for admixing) will be needed to prepare the dose. Prior to dispensing, the pharmacist will remove the TV1.C gp120 and 1086.C gp120 vials from the freezer and allow them to thaw at room temperature. The pharmacist will also remove the $AS01_B$ vials from the refrigerator.

Using aseptic technique, the pharmacist will withdraw 0.5 mL into a 1 mL syringe from the first vial of $AS01_B$. This volume will be transferred into the empty sterilized vial ("preparation vial"). The pharmacist will then repeat this process using the second vial of $AS01_B$. The preparation vial now contains 1 mL of $AS01_B$.

Using aseptic technique, the pharmacist will gently swirl the contents of the vial containing TV1.C gp120 and then withdraw 0.25 mL of TV1.C gp120 from the correct vial and inject it into the preparation vial containing $AS01_B$. The pharmacist will then gently swirl the vial containing 1086.C gp120 after which, using aseptic technique, the pharmacist will withdraw 0.25 mL of 1086.C gp120 from the correct vial and inject it into the preparation vial (which contains TV1.C gp120 and $AS01_B$). After gentle swirling and inversion (do not shake vigorously) the pharmacist, using aseptic technique, will withdraw 0.75 mL of the mixed preparation (100 mcg of each protein mixed with $AS01_B$ Adjuvant System) for dosing into a 3 mL syringe or smaller. The needle should be removed and the syringe capped.

The syringe should be labeled as "Bivalent Subtype C gp120 / $AS01_B$ or Placebo 0.75 mL" and have an overlay to maintain blinding. The syringe must also be labeled for administration in the deltoid of the right arm. The syringe containing study product should be bagged for transport to the clinic where it will be administered. This study product should be administered immediately, defined as within 30 minutes as per IAC recommendations. If this is not possible, the site pharmacist may be permitted to label the syringe with a DO NOT USE AFTER 2 hour date and time from preparation. In this case, the vaccine should be stored at 2°C - 8°C until administration and if not used within 2 hours, it should be discarded.

Any unused portion of vials, preparation vials, or expired prefilled syringes should be disposed of in compliance with local health, safety and environmental requirements.

8.3.6 Bivalent Subtype C gp120 / AS01_B (an admixture of 20 mcg of TV1.C gp120, 20 mcg of 1086.C gp120, and AS01_B)

One vial of TV1.C gp120 protein, one vial of 1086.C gp120 protein, two vials of $AS01_B$, one vial/IV bag/ampule of Sodium Chloride for Injection, 0.9%, and one empty sterilized vial (for admixing) will be needed to prepare the dose. Prior to dispensing, the pharmacist will remove the TV1.C gp120 and 1086.C gp120 from the freezer and allow them to thaw at room temperature. The pharmacist will also remove the $AS01_B$ vial from the refrigerator.

Using aseptic technique, the pharmacist will withdraw 0.5 mL into a 1 mL syringe from the first vial of $AS01_B$. This volume will be transferred into the empty sterilized vial ("preparation vial"). The pharmacist will then repeat this process using the second vial of $AS01_B$. The preparation vial now contains 1 mL of $AS01_B$.

Using aseptic technique, the pharmacist will gently swirl the contents of the vial containing TV1.C gp120 and then withdraw 0.05 mL of TV1.C gp120 from the correct vial and inject it into the preparation vial containing AS01_B. The pharmacist will then gently swirl the vial containing 1086.C gp120 after which, using aseptic technique, the pharmacist will withdraw 0.05 mL of 1086.C gp120 from the correct vial and inject it into the preparation vial (which contains TV1.C gp120 and AS01_B). Using a new syringe, the pharmacist will then withdraw 0.4 mL of Sodium Chloride for Injection, 0.9% and transfer it into the preparation vial (containing TV1.C gp120, 1086.C gp120 and AS01_B). After gentle swirling and inversion (do not shake vigorously) the pharmacist, using aseptic technique, will withdraw 0.75 mL of the mixed preparation (20 mcg of each

protein mixed with $AS01_B$ and 0.9% NaCl) for dosing into a 3 mL syringe or smaller. The needle should be removed and the syringe capped.

The syringe should be labeled as "Bivalent Subtype C gp120 / $AS01_B$ or Placebo 0.75 mL" and have an overlay to maintain blinding. The syringe must also be labeled for administration in the deltoid of the right arm. The syringe containing study product should be bagged for transport to the clinic where it will be administered. This study product should be administered immediately, defined as within 30 minutes as per IAC recommendations. If this is not possible, the site pharmacist may be permitted to label the syringe with a DO NOT USE AFTER 2 hour date and time from preparation. In this case, the vaccine should be stored at 2°C - 8°C until administration and if not used within 2 hours, it should be discarded.

Any unused portion of reconstituted vials or expired prefilled syringes is disposed of in compliance with local health, safety and environmental requirements.

8.3.7 Placebo for Bivalent Subtype C gp120 / AS01_B (Sodium Chloride for Injection, 0.9%)

Using aseptic technique, the pharmacist will withdraw 0.75 mL of Sodium Chloride for Injection, 0.9% into a 3 mL syringe or smaller. The needle should be removed and the syringe capped.

The syringe should be labeled as "Bivalent Subtype C gp120 / $AS01_B$ or Placebo 0.75 mL" and have an overlay to maintain blinding. The syringe must also be labeled for administration in RIGHT deltoid. The syringe containing study product should be bagged for transport to the clinic where it will be administered. The study product should be administered immediately, defined as within 30 minutes as per IAC recommendations. If this is not possible, the site pharmacist may be permitted to label the syringe with a DO NOT USE AFTER 2 hour date and time from preparation. In this case, the vaccine should be stored at 2°C - 8°C until administration and if not used within 2 hours, it should be discarded.

Any unused portion of entered vials or expired prefilled syringes should be disposed of in accordance with institutional or pharmacy policy.

8.3.8 Procedures to preserve blinding

The pharmacist will prepare all doses for administration and dispense to the clinic. In order to preserve blinding, the pharmacist will place an overlay on ALL the syringes.

8.4 Administration

All injections are to be given IM in the deltoid indicated. At sites where registered pharmacists are legally authorized to administer injections, the HVTN CRS may choose to have the pharmacist administer vaccinations.

When preparing a dose in a syringe and administering the dose, consideration should be given to the volume of solution in the needle before and after the dose is administered. Particularly, if the needle used to withdraw the product is replaced prior to vaccine administration, consideration should be given to conserving the full dose of product. The pharmacy and clinic staff members are encouraged to work together to administer the dose specified in the protocol.

All injections are to be given using standard IM injection technique.

For all syringes containing Bivalent Subtype C gp120/MF59 or placebo or Bivalent Subtype C gp120/AS01_B or placebo, the person administering the injection should gently roll the syringe prior to administration of the study product.

If an injection(s) needs to be administered in an alternate body site (eg, thigh) due to a medical contraindication, the injection(s) should not be administered in the same deltoid as the other injection(s). The appropriate study staff should document this clearly. Under this circumstance, this is NOT a protocol violation.

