6.2 Randomization

The randomization sequence will be obtained by computer-generated random numbers and provided to each HVTN CRS through a Web-based randomization system. The randomization will be done in blocks to ensure balance across groups. At each institution, the pharmacist with primary responsibility for dispensing study products is charged with maintaining security of the treatment assignments (except in emergency situations as specified in the HVTN MOP). Randomization will be stratified by geographical region (Southern Africa and US).

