6.3 Blinding

Participants and site staff (except for site pharmacists) will be blinded as to participant treatment group assignments. Study product assignments are accessible to those HVTN CRS pharmacists, DAIDS protocol pharmacists and contract monitors, and SDMC staff who are required to know this information in order to ensure proper trial conduct. Any discussion of study product assignment between pharmacy staff and any other HVTN CRS staff is prohibited. The HVTN SMB members also are unblinded to treatment assignment in order to conduct review of trial safety.

When a participant leaves the trial prior to study completion, the participant will be told he or she must wait until all participants are unblinded to learn his or her treatment assignment.

Emergency unblinding decisions will be made by the site investigator. If time permits, the HVTN 108 Protocol Safety Review Team (PSRT) should be consulted before emergency unblinding occurs.

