8.6 Pharmacy records

The HVTN CRS pharmacist is required to maintain complete records of all study products. The pharmacist of record is responsible for maintaining randomization codes and randomization confirmation notices for each participant in a secure manner.

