9.3 Enrollment and vaccination visits

Enrollment is simultaneous with first vaccination. The time interval between randomization and enrollment should not exceed 4 working days. The HVTN CRS randomizes the participant via the Web-based randomization system as described in the HVTN 108 *Study Specific Procedures*. Circumstances may require a participant's enrollment visit to be changed. This may exceed the 4-day randomization time limit.

At all vaccination visits, the following procedures are performed before vaccination:

- Abbreviated physical examination, including weight, vital signs, and a symptomdirected evaluation by history and/or appropriate physical exam based on participant self-reported symptoms or complaints;
- Assessment of baseline reactogenicity parameters;
- Assessment of concomitant medications (as described in Section 9.2);
- Assessment of any new or unresolved AEs/intercurrent illnesses; and
- Urine or serum pregnancy test (for participants who were born female). Persons who are NOT of reproductive potential due to having undergone total hysterectomy or bilateral oophorectomy (verified by medical records), are not required to undergo pregnancy testing.

Following completion of all procedures in the preceding list, and if results indicate that vaccination may proceed, vaccination is prepared and administered (see Sections 8.3 and 8.4).

Administration of all injections during a vaccination visit must be accomplished within 1 calendar day.

Immediately following vaccination, the participant remains in the clinic for observation. An initial reactogenicity assessment is made at a target of 30 minutes after injection, with an acceptable range of 25-60 minutes. Before leaving the clinic, the participant will be

HVTN 108, Version 2.0 / August 8, 2016

given the 7 day postvaccination symptom log and is instructed on how to complete it. Contacts between the participant and the site staff should take place daily during the first 3 days of the assessment period. Site staff will review the rest of the postvaccination symptom log at the first follow up visit (as described in Section 9.11).

The following procedures will be performed at all vaccination visits. These procedures may be performed prior to or following vaccination:

- Risk reduction counseling (as described in Section 9.8);
- Pregnancy prevention assessment (as described in Section 9.2 and 9.9); and

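### Does letting an unblinded site pharmacist give the injections leave reactogenicity open to unblinded assessment?

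*Combined protocol and SAP*

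**What the plan says.** **Who injects.** Section 8.4 makes pharmacist injection a site option, limited to places where it is legal: "the HVTN CRS may choose to have the pharmacist administer vaccinations". The same section treats pharmacy and clinic as separate groups: "The pharmacy and clinic staff members are encouraged to work together to administer the dose specified in the protocol".

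**Who is blinded.** Section 6.3: "Participants and site staff (except for site pharmacists) will be blinded as to participant treatment group assignments". It adds: "Any discussion of study product assignment between pharmacy staff and any other HVTN CRS staff is prohibited".

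**What the pharmacist knows and must protect.** Section 8.3.8: "The pharmacist will prepare all doses for administration and dispense to the clinic", with an overlay on every syringe. Section 8.6: "The pharmacist of record is responsible for maintaining randomization codes and randomization confirmation notices for each participant in a secure manner". Section 6.2: "the pharmacist with primary responsibility for dispensing study products is charged with maintaining security of the treatment assignments".

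**Who assesses.** Table 9-1 in Section 9.11 gives the baseline and 25-60 minute checks to HVTN CRS staff and every later row to staff or participant. Section 9.3 adds: "Site staff will review the rest of the postvaccination symptom log at the first follow up visit". Section 9.11 has reactions above mild generally seen by a clinician within 48 hours, and Section 11.2.2 gives adverse event evaluation to clinic staff.

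**What depends on it.** Severe reactogenicity to day 7 is part of primary endpoint 1 (Section 5.1), and severity is compared between groups by Kruskal-Wallis tests (Section 6.4.3.1).

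**The concern.** Read together, these sections seem to leave a route to unblinded assessment. The pharmacist has prepared the dose, so the overlay hides nothing from that person. The Section 6.3 ban on discussion speaks of pharmacy staff and other CRS staff, which places pharmacists within the CRS staff category, and Table 9-1 uses that category without a qualifier. Taken literally, a pharmacist who injects could also make the 25-60 minute check. The ban does not name participants either, and an injector is in direct contact with them.

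Elsewhere the protocol guards against this kind of problem. Section 11.2.3 keeps the sponsor's medical officer blinded when relatedness is judged, because safety is a primary endpoint. Section 11.4.1 has HVTN Core's daily safety reviews done blinded.

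At stake is the between-group comparison of reactogenicity severity. An assessor who knows the assignment, or cues passed to a participant, could shift the reporting or grading of subjective symptoms.

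**Working it through.** No sample size, power or rate is in dispute, so the check is to count what is exposed and then read the sections against each other.

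**Subjective share of the endpoint.** Section 5.1 lists 12 solicited items: pain, tenderness, erythema, induration, fever, malaise/fatigue, myalgia, headache, nausea, vomiting, chills and arthralgia. The footnote to Table 11-1 classes 8 of them as subjective: pain, tenderness, malaise/fatigue, myalgia, arthralgia, chills, headache and nausea. 8/12 = 67%.

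**Rows that only staff can complete.** Table 9-1 has 3 rows for day 0 (baseline, early, rest of day) and 7 for days 1 to 7: 3 + 7 = 10. Baseline and early are staff-only, which is 2 of 10. Without baseline, 9 rows follow the injection: 1 is staff-only and 8 are staff or participant. Over four vaccinations that is 4 × 9 = 36 post-injection rows, of which 4 × 1 = 4 are staff-only and 4 × 8 = 32 can be recorded by the participant. These counts show who may record what; they do not measure bias.

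**How the early row enters the analysis.** Section 6.4.3.1 counts each participant once per symptom, at the maximum severity over all injection visits. For a participant graded too low at the early check, any higher grade in another row replaces it. For one graded too high, the error matters only if it exceeds every other row. The early row is therefore not the sole determinant of anyone's result.

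**Blinding of the assessor.** The assessor is a member of site staff, the clinic or the participant (Sections 9.3, 9.11 and 11.2.2). Section 6.3 blinds participants and all site staff except pharmacists. So every assessor other than a pharmacist is already required to be blinded. Sections 8.4 and 9.11 do not repeat the rule, but Section 6.3 governs them.

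**Whether the pharmacist is ever an assessor.** Section 8.4 concerns injection only and distinguishes pharmacy from clinic staff. Section 11.2.2 names clinic staff, and Section 9.11 names a clinician for reactions above mild, the range that contains the severe events of the primary endpoint. No section ties a pharmacist to an assessment.

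**Cues to participants.** Section 6.3 requires participants to be blinded, and Section 6.2 makes the dispensing pharmacist responsible for the security of the assignments. A pharmacist who hinted at the assignment would breach these two sections as they stand, even though the ban on discussion names only staff.

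**What remains.** No sentence expressly stops a pharmacist from acting as CRS staff in Table 9-1. Section 12 refers clinical and safety assessments, and unblinding of staff and participants, to DAIDS and HVTN procedures. Section 8 refers pharmacy practice to the DAIDS Pharmacy Guidelines. Those manuals are not available here, so the sentence may already exist.

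**The case for a change.** The best case for acting is that the gap is real on the text, the endpoint is primary, and one sentence would close it with no new data, visits or analyses. Participants stay in the clinic after injection, so the injector may be close by when the early check is made. Self-report removes staff grading but not cueing. The questionnaire on which product participants believe they received is scheduled only at Months 6 and 12 (Appendix H), so it could reveal a broken blind but not prevent one.

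Most of this is true as description. The literal reading of Table 9-1 stands, and unintended cues from an unblinded injector cannot be ruled out. The step from there to a defect does not stand. It requires a site to combine two roles that the protocol describes separately, against the evident purpose of Section 6.3. The sponsor-level blinding in Sections 11.2.3 and 11.4.1 shows no inconsistency, since Section 6.3 supplies the site-level counterpart for everyone except the pharmacist.

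The remedy also has a cost if drawn widely. A rule barring anyone with access to an assignment from grading or causality could exclude a site investigator who had made an emergency unblinding under Section 6.3. A sentence confined to pharmacists would avoid that, but it would only write down what the division of roles already implies.

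**Conclusion.** No change follows. This is missing detail that sites can be expected to fill sensibly. If the plan is followed as written, with blinded clinic staff assessing and blinded participants recording, the reactogenicity comparison is sound.

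The residual is confined to sites that use the Section 8.4 option and, within them, to a pharmacist who also assesses. The documents give neither the number of such sites nor any instance of a pharmacist assessing, so no bias can be shown or sized. The one post-injection row in 9 that only staff can complete is the part most directly exposed. Laboratory safety measures and the adequate take/potency decision, which rests on 11 assay endpoints (Section 6.1.2), are little affected.

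This conclusion assumes that sites keep dispensing and clinical assessment apart, as Sections 8.4 and 11.2.2 describe, and that Section 6.3 is applied to every other assessor. Evidence that pharmacists were grading reactions at some sites would reopen the question.
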